### 7.2 C-Scan Technology

The technology of the Check-Cap Imaging System is based on a low dose radioactive (RA) sealed source embedded in the C-Scan capsule which radiates X-Rays through a collimator to all directions. The capsule is designed to start scanning once it reaches the cecum and the X-ray is emitted when the capsule is propagating along the colon during contraction of the walls. While stationary (which is most of the time) the capsule is set at an idle mode and the radiation X-ray source is blocked by the collimator. The transit time of the capsule in the colon might vary from 24-100 hours, pending the typical bowel activity of the subject. The capsule is powered by onboard batteries and is designed to operate up to 100 hours.

	Document Title	Clinical Investigational Plan For Study CL-SY-02-0096		
	Document No.	DOC001593	Revision	03

The C-Scan is designed to be ingested without any cleansing of the colon and travel through the gastrointestinal (GI) tract naturally while the subject continues daily activities, including eating normally. During C-Scan procedure the subject swallows a capsule and capsule travels painlessly through the gastrointestinal tract, identifying polyps, the precursors of colorectal cancer. In order to increase the contrast of the colon's walls and to differentiate them from their content, it is essential to increase the stool's contrast by ingesting radio-opaque material. It is a standard procedure using approved Iodine based liquids, contrast agents such as (Telebrix or Omnipaque) at the discretion of the hospital similar to the preparation to abdominal computerized tomography (CT).

During the passage of the capsule in the gastrointestinal tract, it transmits information to a recorder attached to the back. In order to collect data about the instantaneous localization of the capsule traveling in the colon additional sensors are embedded in the recorder on the back side. A commercial wrist watch is supplied (optional) with the C-Scan system for use by the subject during the procedure. The watch is tuned to 'listen' and display the information transmitted from the capsule to the Track. The watch is a monitoring tool to optimize data interpretation during the clinical study and is not an integral part of the C-Scan system.

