### 8.1 Clinical Study Protocol C-SY 00093

A multicenter clinical study was conducted at four sites in Israel in 2017. Sixty-Six subjects were enrolled (40 Men (61%) and 26 Women (39%), BMI <40), of which three failed to ingest the capsule, including one subject with a known swallowing disorder which was not disclosed to the study team during screening. Forty-Three had polyp(s) (65%) as indicated by their prior recent colonoscopy reports and the other 23 were considered as average risk population without any prior information about their colon.

All study procedures were completed and feedback from most subjects was positive and reassuring that the procedure was well-tolerated.

All capsules (except one) were collected and retrieved for QA inspection. They were all found to be intact and hermetically sealed.

The total transit time (TTT) is measured in hours between capsule ingestion to excretion. The TTT is the sum of 3 distinct sections:

- Time until reaching the caecum
- Time capsule dwells in the caecum
- Time of colon passage until excretion

The following table is the summary of all 63 cases in whom the study was completed (3 did not ingest). The standard deviation (STD) is quite high due to the considerable variability in bowel motility.

	Total Transit Time	Time to Caecum	Time in Caecum	Passage in colon
Average (hours)	52.3	15.9	16.8	16.5
STD	32.9	13.7	18.8	12.1

Table 2: Average transit time of the 3 sections of the GI tract and the standard deviation in each one.

There were no cases of C-Scan capsule retention (medical definition of Capsule retention is when TTT is longer than 300 hours – about 13 days).

The C-Scan is designed to operate continuously for 100 hours. There was one case in which the capsule was retained for 100-200 hours and then removed during the follow-up colonoscopy procedure

	Document Title	Clinical Investigational Plan For Study CL-SY-02-0096		
	Document No.	DOC001593	Revision	03

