### 10.4 Secondary Outcome Measures

- Subject compliance will be assessed by
  - Non-compliance rate throughout the study via diary completion by the subject Specific questionnaire completed by remote subject monitoring (via telephone)
- Subject satisfaction will be established by:
  - Designated questionnaire that focuses on patient's impressions regarding tolerance and potential safety concerns. Acceptance criteria was defined as average score >3.5 (1- low satisfaction to 5- high satisfaction), which represent high satisfaction with the safety and tolerance of the C-scan system.
  - Comparing patient's satisfaction with colonoscopy procedure.
- Collecting procedure related data:
  - Technical performance in normal daily routine.
  - Segmental transit time.
  - Procedure duration.
  - Bowel movements.
  - Agreement between C-Scan and colonoscopy with respect to the presence/absence of colonic polyp(s) [Note: C-scan data not to be used for clinical decision making in the care of patients, for this clinical study].
  - Inter-observer variability in the detection of significant clinical findings on a 'per patient' decision
- Battery life Assessment
  - Assessing adequate power supply for complete scan of the colon: length of capsule operation lifetime with respect to the lifetime specification of 100 +/- 10% hours.
- Device performance
  - Assessing colon model by the physician reviewers as presented on C-Scan View (e.g., normal, partial, right side missing, etc.).
  - Collecting data to improve the product's algorithm.

	Document Title	Clinical Investigational Plan For Study CL-SY-02-0096		
	Document No.	DOC001593	Revision	03

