### **13.7 Follow Up 2: Capsule excretion and collection**

#### **13.7.1 Capsule Return**

Capsule procedure is completed upon capsule excretion or system auditory indication of 'End of Procedure'. Subjects will be instructed to inform the study coordinator or designee upon capsule excretion.

The subjects will be provided with a dedicated capsule collection kit, to assist the subjects in collecting the capsule. Subjects will be instructed to retrieve the capsule upon excretion. Return packaging and instructions will be provided. The subject will return with the Kit the diary, the questionnaire and all unused materials.

In case of doubt regarding capsule excretion, and per physician discretion, subjects may be referred to abdominal X-Ray to confirm capsule excretion.

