### 14.1.3 Operational Analysis Set

Technical or operational failures that will be discarded from the trial statistical analysis will include all cases where the system did not function as expected:

- Capsule operational failure.
- Track operational failure.
- Subject's noncompliance with procedure requirements

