### 14.1.4 Data analysis

Descriptive statistics for all parameters will be calculated. For continuous parameters descriptive statistics including mean, standard error, median, minimum, and maximum values will be reported overall and at each time-point. For ordinal parameters, counts and percentages may be reported in addition to the mean, standard error, median, minimum, and maximum values. Categorical parameters will have counts and percentages reported overall and at each time-point.

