##### 15.1.3.1 Possible Scenarios and Recommended Physician's Action:

In all cases the physician may opt to use local protocols for patients administered with gastrointestinal capsules; medical intervention or lack of, which remains at physician's discretion.

- **Capsule is Not Found After C-Scan® Track indicates it was expelled**
  - Advise the subject to look in the toilet. If it is found, the subject should notify the clinic which will arrange for the collection of the C-Scan system.
  - If the capsule is not found, the subject should speak with a physician at the clinic as there is a chance it was not expelled despite the positive indication. The physician might recommend using a laxative at home to try to expel the capsule. Make sure that the subject knows to use the collection kit during any bowel movements. Or, the physician investigator may recommend the subject to come to the clinic for a physical exam, and depending on findings, consider abdominal X-Ray imaging.
- **Capsule Not Expelled After 4 Days (~100 hours)**
  - If 4 days have passed and the capsule was not expelled, the subject should speak with a physician at the clinic (if needed, be sure to initiate a contact with the patient). The physician might recommend using a laxative at home to try to expel the capsule. Make sure that the subject knows to use the collection kit during any bowel movements. Or, the physician investigator may recommend the subject to come to the clinic for a physical exam, and depending on

	Document Title	Clinical Investigational Plan For Study CL-SY-02-0096		
	Document No.	DOC001593	Revision	03

findings, consider abdominal X-Ray imaging.

- Intervention, based on the physician's decision and imaging of the capsule's location, may include: use of laxatives, fibers, removal by colonoscopy, or by surgery.
- In case that the capsule is retained in the small bowel, as suspected according to the X-Ray imaging, the recommended Intervention, based on the physician's decision, may include: use of laxatives, prokinetic drugs, removal by SB enteroscopy (with double balloon if available) or by surgery.

- **Capsule lost communication (no flashing lights on Track) at any time between ingestion and 100 hours:**
  - Advise the subject to verify that the batteries in the Track are in position and the compartment is well secured
  - Verify that the patient is still wearing the Track on his/her back

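### Battery outcome: most capsules are likely to leave the body before the 100 h specification can be tested, the planned mean and median would mainly reflect transit, and the exclusion rule on a plain reading drops early depletions

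*Combined protocol and SAP*

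**What the plan says.** - Section 10.4 lists a battery life assessment, asking whether power suffices for a complete colon scan. The measure is "length of capsule operation lifetime with respect to the lifetime specification of 100 +/- 10% hours", that is, 90 to 110 h. No pass/fail rule is attached.
- Section 13.7.1: "Capsule procedure is completed upon capsule excretion or system auditory indication of 'End of Procedure". What that signal marks is not stated.
- Section 14.1.4: "For continuous parameters descriptive statistics including mean, standard error, median, minimum, and maximum values will be reported". For categories, "Categorical parameters will have counts and percentages reported overall and at each time-point", but no categorical battery measure is defined.
- Section 14.1.3 describes the technical or operational failures "discarded from the trial statistical analysis will include all cases where the system did not function as expected". Its list names capsule failure, Track failure and subject noncompliance. It makes no exception for the battery outcome and does not mention depletion.
- Section 16.1.4 counts failure to meet performance specifications as a malfunction.
- The design figure is worded in two ways: "The capsule is powered by onboard batteries and is designed to operate up to 100 hours" (section 7.2) and "The C-Scan is designed to operate continuously for 100 hours" (section 8.1).
- Section 8.1 reports one earlier capsule whose batteries had run out (hour not given), two faulty capsules that stopped working, and four transits longer than 120 h.

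**The concern.** Operating lifetime is fully observed only if the battery runs out before the capsule leaves the body. Otherwise the recorded time is the transit time, and battery life is known only to exceed it. The document does not say how such capsules enter the summary. It mentions neither censoring nor running returned capsules to depletion; section 8 says earlier returned capsules were checked for sealing and structure.

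Two things are at stake. A mean near 50 h set beside a 100 h specification could be read as battery failure when it only shows that subjects excreted the capsule. In the other direction, if depletion before 90 h is discarded as a case where the system did not function as expected, early power failures disappear from the one outcome designed to count them.

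**Working it through.** The plan gives no computed figure to reproduce; section 14.1.1 states that the sample size does not come from a power analysis. What follows is illustrative.

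**Inputs.** From the document: N up to 45; specification 90 to 110 h; total transit mean 52.3 h and SD 32.9 h in 63 completed cases (section 8.1, Table 2). Because some earlier capsules were removed or hurried out, this is time to excretion or removal, T. Assumed: the shape of T, and a fixed battery life L of 80 h or 100 h.

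**Model.** Observed operating time is X = min(T, L). The mean of X is the integral of P(T>t) from 0 to L, and its standard error (SE) is SD(X)/√45. Each shape is matched to the mean and SD. For the lognormal:
- σ² = ln(1 + (32.9/52.3)²) = 0.333, so σ = 0.577
- μ = ln 52.3 − 0.333/2 = 3.790
- P(T<90) = Φ((ln 90 − 3.790)/0.577) = Φ(1.23) = 0.890

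The gamma has shape 2.53 and scale 20.7. The Weibull has shape 1.63 and scale 58.4.

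| Quantity | Lognormal | Gamma | Weibull |
|---|---|---|---|
| P(T<90 h) | 0.890 | 0.875 | 0.868 |
| At risk at 90 h, of 45 | 4.9 | 5.6 | 6.0 |
| At risk at 100 h, of 45 | 3.6 | 4.0 | 4.1 |
| Mean X, L = 80 h (SE) | 47.40 (3.1) | 47.42 (3.4) | 47.55 (3.6) |
| Mean X, L = 100 h (SE) | 49.63 (3.7) | 49.97 (4.0) | 50.24 (4.2) |
| Gap in means | 2.23 | 2.55 | 2.69 |
| Median X, either L | 44.3 | 45.6 | 46.7 |
| P(maximum reaches 100 h), L = 100 h | 0.9755 | 0.9841 | 0.9861 |
| Depleted before exit if L = 80 h, of 45 | 6.9 | 7.9 | 8.5 |

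The maximum row is 1 − P(T<100)^45. Depleted capsules are kept in all rows. A battery 20 h short moves the mean by less than one SE and leaves the median unchanged. The maximum does respond, since with L = 80 h it cannot exceed 80 h.

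**Other transit assumptions.**
- Mean 47 h, SD 25 h: about 94% leave before 90 h, 2.7 to 2.8 are at risk there, and the gap is 1.25 to 1.29 h. The chance that the maximum reaches 100 h falls to 0.76 to 0.83.
- Mean 58 h, SD 38 h: 81% to 85% leave before 90 h, 6.8 to 8.4 are at risk, and the gap is 3.1 to 3.8 h against an SE of 3.9 to 4.5 h. This case gives 6.5% to 7.2% beyond 120 h, nearer the reported 4/63 = 6.3% (denominator assumed) than the main fit's 3.9% to 4.2%.

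**Effect of the exclusion, L = 80 h.** Take 7 or 8 depletions.
- All 45 kept: 38/45 = 84.4% (exact 95% CI 70.5% to 93.5%) or 37/45 = 82.2% (67.9% to 92.0%) are powered at exit.
- Depleted capsules removed: 38/38 or 37/37 = 100%, with exact lower limits 90.7% and 90.5%.

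**Does censoring repair it?** In 4,000 simulated studies of 45 (lognormal T, 20% of batteries failing at about 70 h, so the true proportion lasting 90 h is 0.80), Kaplan-Meier with every depletion kept averaged 0.80 (SD 0.14). With depletions before 90 h dropped, it was 1.00 in every study.

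**Limit of information.** If all 5 or 6 capsules at risk are working at 90 h, the one-sided 95% upper bound on failure before 90 h, from those capsules alone, is 1 − 0.05^(1/5) = 45% or 1 − 0.05^(1/6) = 39%.

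**The case against.** A reader might infer that the planned summary cannot tell an 80 h battery from a 100 h one. That goes too far. Section 14.1.4 includes the maximum, and under fixed battery lives it separates the two about 97.5% to 98.6% of the time. This part of the objection stands, with the limit that the maximum depends on the few longest-running capsules, weakens with shorter transits, and would weaken further if battery life varies.

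A reader might also infer that section 14.1.3 expressly removes depleted batteries. It does not: depletion is not named and capsule operational failure is not defined. The exclusion is a plain reading, supported by the specification in section 10.4 and the malfunction definition in section 16.1.4. The 100% result follows by construction once depleted capsules go, so it shows the direction of the distortion and not an expected size. Nor do the documents establish that depletion within 90 to 110 h is discarded. Section 16.1.4 lists a caecal stay of about 100 h or more, beyond the operating time, among its malfunction examples, but section 14.1.3 does not refer to that list.

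The lower-bound argument rests partly on silence. Used units go back to the sponsor (section 19), and nothing rules out a bench run-down. Nothing provides for one either, so operating lifetime is undefined for capsules excreted while working.

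The section 15.1.3.1 scenario, "Capsule lost communication (no flashing lights on Track) at any time between ingestion and 100 hours", names no cause, but it guides patient management and does not show that causes go unseparated in the data. Finally, battery life is not among the secondary objectives in section 10.2 and has no acceptance criterion. That limits the weight of the point without removing it.

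**Conclusion.** The point holds in a limited form. With transit like the earlier study's, about 87% to 89% of capsules would leave before 90 h. The planned mean and median would then mainly reflect transit, and the specification would be informed by about 5 to 6 of 45 capsules. On a plain reading of section 14.1.3, depletion before 90 h would be discarded from the battery outcome.

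These sizes rest on the earlier study's mean and SD, three assumed shapes and assumed fixed battery lives. Under the shorter and longer transit cases the shift in the mean stays below one SE. The one depletion reported earlier has no stated hour, so it does not show that batteries fall short. The outcome is minor, secondary and descriptive, in an unpowered pilot, and a reader should not infer that this point bears on the primary safety result. It is still worth correcting, because the change is small and the figure should describe batteries.

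**What to change.** In section 14, state that the section 14.1.3 exclusion does not apply to the battery outcome and that all ingested capsules are included. Then report two measures.

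- **Adequacy:** the proportion still powered at excretion or removal, with an exact 95% CI. Describe it as depending on transit and battery together, not as a test of the specification. If every battery lasted exactly 100 h, about 8% to 9% (3.6 to 4.1 of 45) would still run out before excretion.
- **Specification:** the number of depletions before 90 h, with operating time right-censored when a working capsule is excreted or removed, and numbers at risk at 90 and 100 h. Depletion at or after 90 h is not a failure to reach the lower limit. Removal of a capsule that has already stopped is not censoring. State the assumption that transit is unrelated to battery life, since section 7.2 says the capsule idles while stationary.

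Report non-battery and unknown-cause shutdowns separately, and show adequacy with the unknowns counted both ways. For a hypothetical 45 ingested with 2 depleted and 2 unknown: 43/45 = 95.6% (84.9% to 99.5%) if unknowns are not counted as failures, and 41/45 = 91.1% (78.8% to 97.5%) if they are.

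Also state how the End of Procedure signal is classified, that functioning as expected is judged for this outcome against the section 10.4 range, whether returned capsules will be run to depletion, and that with about 5 to 6 capsules at risk at 90 h the study cannot confirm the specification.

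**Cost:** analysis wording and possibly one CRF status field (powered at exit, battery depleted, other shutdown, unknown). The Track stores all procedure data (section 9.1.1) and units return to the sponsor, so causes can be looked into. No added visits or subjects.

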and in another case it was initiated by the sponsor since the batteries in the capsule were already depleted and no additional benefit was expected from the procedure. In two other cases, drugs (*Picolax*) were used to expedite the expulsion of faulty capsules (that stopped working). In all four cases the total time was less than 200 hours. In one case the capsule was not retrieved by the patient at the end of the procedure and, probably lost in the sewage system. Abdominal X-ray on the following day confirmed that the capsule was expelled with no residual in the GI tract images. All cases were completed uneventfully.

Several adverse events were reported including one case of irritating sensation in the esophagus that lingered for hours after capsule ingestion, skin irritation (under the stickers), soft stool, abdominal pain, headache, radiation level (body dose) was significantly higher than the typical dose of 50 uSV and four cases in which the transit time was longer than 120 hours. Three SAE events occurred including one hemorrhage/hematoma seen on abdominal wall, one post-colonoscopy bleeding and one post-colonoscopy abdominal pain. All SAE were non-related to device or C-Scan procedure and resolved without medical intervention. Several technical malfunctions occurred during the study, none of which resulted in harm to the subject but did not provide any data regarding the performance of the C-Scan system. During the study, updates were made to the system software to continue to optimize the algorithm and the ability to collect additional physiological data.

This study demonstrated that the C-Scan procedure was safe as no device- related serious adverse event occurred in any C-Scan clinical trial and the procedure was well-tolerated by the participating volunteers. The primary end point of safety for the C-Scan system was demonstrated. The primary end point for performance in terms of Positive Percent Agreement resulted in 44% capsule vs 37% for FIT. The protocol target was set at 55%, hence superiority was demonstrated with a lower than expected result. The result of Negative Percent Agreement was 89% vs. a set target of 75%, hence target surpassed the expected result.

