### 10.2 Secondary Objectives

- To evaluate subject's compliance
- To evaluate subject's satisfaction
- To collect data to improve the product's algorithm

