## 14 STATISTICAL ANALYSIS

### 14.1.1 Sample Size Considerations

This is a pilot safety study; therefore, sample size is not determined by power analysis. Up to 45 subjects will be recruited to the study.

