#### 16.1.4 Device Malfunction/Failure

Malfunction means the failure for device to meet its performance specifications or otherwise perform as intended. In general, this is related to a component of the system not functioning as intended to provide the required outputs. Examples of a device malfunction include:

- C-Scan capsule does not traverse through the colon – the scanning of the colon is aborted prior to reaching the rectum or the image scan density throughout the colon is inadequate for clinical interpretation
- C-Scan shield does not retract – temporarily excessive radiation from the capsule
- C-Scan does not record tracking through colon- temporarily or continuous loss of tracking of the capsule by the recorder, causing inadequate or partial activation of the scanning function
- Corrupted data – the stored data in the recorder is corrupted and cannot be interpreted by the C=Scan View for clinical data analysis
- External interference – External electromagnetic interference (Hybrid cars, generators or other sources) cause interference to the communication with the capsule or to the tracking circuitry, thus causing periods of lost data during the procedure

	Document Title	Clinical Investigational Plan For Study CL-SY-02-0096		
	Document No.	DOC001593	Revision	03

- Physiological causes – subjects who fail to ingest the capsule, or subjects in which the capsule dwells in the caecum for a period of ~100 h or more, thus exceeding the operation time of the C-Scan system

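### Technical-failure discards under Section 14.1.3 can be decided after the colonoscopy result is known, and no rule says which read counts, so agreement with colonoscopy could be inflated

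*Combined protocol and SAP*

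**What the plan says.** **Discard rule.** Section 14.1.3 refers to "Technical or operational failures that will be discarded from the trial statistical analysis" and applies this to all cases of improper system function. It names three kinds: capsule failure, Track failure and subject noncompliance. It gives no numeric limit, names nobody to decide, and does not say when the decision is made relative to colonoscopy or FIT.

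**Malfunction examples.** Section 16.1.4, in the adverse-event chapter, gives examples of malfunction. One is that "the image scan density throughout the colon is inadequate for clinical interpretation", with no figure attached. Another, under physiological causes, is a capsule that stays in the caecum for about 100 hours or more. Neither section refers to the other.

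**Two uses of one cohort.** Section 10.2 has the secondary objective "To collect data to improve the product's algorithm", and Section 10.4 repeats it under device performance: "Collecting data to improve the product's algorithm". Section 10.4 also lists agreement with colonoscopy on polyp presence, and reviewer grading of the colon model. There is one cohort (Section 14.1.1: "Up to 45 subjects will be recruited to the study") and no division into development and test subjects.

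**Reading.** Under Section 13.10 the technical team checks the downloaded data for completeness once the capsule is returned. The View workstation then reconstructs the images, bookmarks may be prepared, and three reviewers decide on polyps by majority. No software version, lock or rule on re-reading is given.

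**Precedent.** Section 8.1 says of the previous study: "During the study, updates were made to the system software to continue to optimize the algorithm and the ability to collect additional physiological data".

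**The concern.** Whether a scan is too poor to interpret is a judgement. If it is made after colonoscopy has shown a polyp that C-Scan missed, the miss can become a technical failure and drop out of the denominator. Section 17.1 has procedure reports, such as the colonoscopy report, passed to the sponsor. The sponsor's side is also where development takes place, so the information needed for such a decision would be at hand.

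A second route is reprocessing. If a case is reconstructed again and re-read, the plan does not say which result enters the agreement table.

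Blinding the three readers would close neither route, because both act on which cases and which images reach the table. At stake are the agreement figure and the colon-model grades. The latter are exposed even without bad intent: the scans most likely to be called failures are those that would have been graded partial or incomplete.

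**Working it through.** **1. No planned figure to reproduce.** Section 14.1.1 states: "This is a pilot safety study; therefore, sample size is not determined by power analysis". The plan sets no agreement target, interval or test for this study. The check is therefore a reading of the rules plus an illustration of size.

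**2. Does any rule block a discard that depends on the result?**
- Section 14.1.3 gives no threshold, decider or timing.
- Section 16.1.4 has one number (about 100 hours in the caecum), but it concerns dwell time and is not tied to the discard rule. Its scan-density example has no number.
- Section 10.4 has a battery specification of 100 hours ± 10%. That is a yardstick for an outcome, not a discard rule.
- Section 13.10 has a completeness check at a suitable time, but does not make it the discard decision or lock it.
- Section 13.6.1 has FIT done before or during the capsule procedure and reported to the study team. Site staff may therefore know the FIT result when the capsule comes back.

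The answer is no.

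**3. Does any rule fix which read counts?** Section 13.10 describes one pass through reconstruction and majority reading. It neither forbids a second pass nor says which would be used.

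**4. Size of the discard effect.** Let D be the subjects with polyps, T those detected, and k the misses discarded.

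Positive agreement before = T/D; after = T/(D − k); inflation = (T/D) × k/(D − k).

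Hypothetical counts D = 20, T = 9, k = 5: before 9/20 = 45%; after 9/15 = 60%; inflation 0.45 × 5/15 = 15 percentage points. Discards unrelated to detection would leave the expected value at 45%.

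**5. Range.** The number of polyp-positive subjects is not given. I assume 30%, 50% or 65% of 45; the top value is the previous study's share (43/66 = 65%, Section 8.1). T is set near that study's 44% positive agreement.

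| D | T/D | 2 misses dropped | 4 misses dropped | 6 misses dropped |
|---|---|---|---|---|
| 14 | 6/14 = 43% | 6/12 = 50% | 6/10 = 60% | 6/8 = 75% |
| 22 | 10/22 = 45% | 10/20 = 50% | 10/18 = 56% | 10/16 = 63% |
| 29 | 13/29 = 45% | 13/27 = 48% | 13/25 = 52% | 13/23 = 57% |

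The shift runs from about 3 points (29 subjects, two dropped) to about 32 points (14 subjects, six dropped). Sampling error is also wide: the exact 95% intervals before any discard are 18–71%, 24–68% and 26–64%. The discard shift differs in that it always goes the same way and no interval would show it.

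**The case against.** The strongest reply is that this is a pilot safety study. Its primary outcome is adjudicated SAEs, agreement is one descriptive item among the procedure data, and no performance target is set. That stands and limits the weight of the point.

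A reader might go further and infer that agreement will be measured on the very data used to tune the algorithm, and might put a figure on the optimism by simulating a re-tuned cut-off. The documents do not support this. They speak of collecting data for improvement, which fits development of a later version. No section plans to retune or re-score these subjects. The polyp call is a majority of three human readers, with no score or cut-off described, so such a simulation would not model this plan. The Scan Control Algorithm acts while the capsule is moving (Section 9.1.1), so a finished case cannot be rescanned. A change to it during the study would mix versions across subjects, which is a different problem. Only reconstruction and bookmarks could be redone for an existing case.

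Two further replies are partly right. The link from the malfunction examples in Section 16.1.4 to the discards in Section 14.1.3 is an inference, since neither cites the other. And colonoscopy follows the capsule procedure (Section 11.1), so the completeness check would often come first. But the plan does not require that order, and does not make that check the point at which the discard is decided.

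**Conclusion.** The point holds as a gap in the rules, not as evidence of planned tuning. As written, Section 14.1.3 allows a missed polyp to be discarded as a technical failure after colonoscopy is known. Section 13.10 leaves open which read counts. Software changes during the previous study show that the second route is not far-fetched, though one study is not proof of a practice.

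The effect would be upward bias in positive agreement and in the colon-model results. Its size depends on how many misses are discarded: 15 points in the hypothetical example, and about 3 to 32 points over the assumed range. These counts are illustrations, not forecasts. The primary SAE outcome does not depend on this mechanism. The change is worth making because an agreement figure from this pilot could inform the next study and the protection is cheap.

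**What to change.** Amend Sections 13.10 and 14.1.3 as follows.

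- **(a) Lock the failure call.** Each technical-failure or inadequate-density call is made and locked at the completeness check already done on capsule return, by existing staff who have not seen that subject's colonoscopy or FIT result.
- **(b) Fix the read that counts.** Only the first majority read enters the agreement analysis, and it is made before that subject's data are released for development. Any reprocessed result is labelled as development.
- **(c) Show the effect of discards.** Report agreement with and without the discarded cases, and state how a discarded case without a read is counted.
- **(d) Record versions.** Record the Scan Control Algorithm and View version for each subject. If a version changes, show results by version.

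A full software freeze is not needed for this purpose and would be a real trade-off in a development pilot. The cost is protocol wording, one CRF field and a short delay before the data can be used for development. No subjects or procedures are added.
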